9.0 MONITORING OF PATIENTS

9.1 Table of Required Observations

Table 7 Required observations

	Baseline	Day 1	Weeks 1-6	Weekly	Day 22	Off Treatment (within 7 days)	30 Day Follow-Up
BAL101553			6				
Corticosteroid Dose Evaluation	1					8	
Prior and Concomitant Medications	1,16			3		8	
AE Evaluation	1			3		8	5,12
Brain MRI	1					8	
H&P/Neuro Exam	1				7	8	
KPS	1				7	8	
Mini-Mental State Examination (MMSE®)		20		3, 20			
Vital Signs	1,4			3,4,14		4,8	
CBC, Diff, Platelets	1			2,3		2,8	
Serum Chemistry	1,10			3,10,13,15		8,10	
Cardiac troponin	1			3,15		8	
Echocardiography, cardiac MRI or MUGA	1						
APTT or PTT and INR	1						
Serum Pregnancy Test	9						
ECG	1			17		(8, 17)	
Archived Tumor Tissue	11						
Blood Samples for PK Analyses		18			18		
Study drug dispensing		19		3, 19			

1. All baseline measurements must be done after obtaining written informed consent and must be performed within 14 calendar days prior to first treatment administration except for the baseline MRI, which may be obtained within 21 days prior to first study drug administration, and the corticosteroid dose evaluation, which should be obtained within 5 days prior to the baseline MRI.
2. If ANC < 1500 or platelets < 100,000, CBCs/differentials will be repeated twice a week until counts are recovered (ANC \geq 1500 or platelets \geq 100,000) per protocol. If counts are recovered (ANC \geq 1500 or platelets \geq 100,000) on day of scheduled drawing, do not repeat until next scheduled protocol study visit.
3. ± 1 day
4. Including blood pressure, respiratory rate, heart rate, temperature, weight, height. Weight and height are required at baseline only.

Phase I Study to Determine the Safety and Tolerability of the Oral Microtubule Destabilizer BAL101553 in Combination with Standard Radiation in Patients with *MGMT* Promoter Unmethylated Newly Diagnosed Glioblastoma

ABTC # 1601

NCI # ABTC-1601

PI: [name]

5. Adverse events must be followed for at least 30 days from last dose of BAL101553.
6. BAL101553 is administered orally every day during radiation therapy (see Section [4.4.1](#)). Patients are required to keep a capsule diary (see [Appendix I](#)).
7. ± 3 days
8. Evaluations are to be performed within the 7 days following the off-treatment date, unless indicated. Evaluations that do not need to be repeated include: MRI if performed within the 14 days prior to the off-treatment date; H&P/neuro, KPS, or labs if performed within the 5 days prior to the off-treatment date.

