10.0 OFF-TREATMENT/OFF-STUDY CRITERIA

Each subject has the right to withdraw from the study at any time without prejudice. The Investigator may discontinue any subject's participation for any reason, including AEs or failure to comply with the protocol (as judged by the Investigator, such as compliance below 80%, failure to maintain appointments, etc.).

Should a subject withdraw from the study, the reason(s) must be stated on the case report form and a final evaluation of the subject should be performed.

Patients who go off treatment must be followed for AEs for at least 30 days from the last dose of BAL101553.

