PI: [name]

Note: Subjects with non-measurable disease cannot have a partial response. The best response possible is stable disease.

Stable Disease (requires all of the following):

- a) Does not qualify for CR, PR, or progression.
- b) The designation of stable disease requires a minimum of 4-week duration.
- c) All measurable and non-measurable sites must be assessed using the same techniques as baseline.
- d) Stable non-enhancing (T2/FLAIR) lesions on same or lower dose of corticosteroids compared to baseline scan. In the event that the corticosteroid dose was increased for new symptoms and signs without confirmation of disease progression on neuroimaging, and subsequent follow-up imaging shows that this increase in corticosteroids was required because of disease progression, the last scan considered to show stable disease will be the scan obtained when the corticosteroid dose was equivalent to the baseline dose.
- e) Stable clinically.

Progressive Disease (defined by any of the following):

- a) $\geq 25\%$ increase in sum of the products of perpendicular diameters of enhancing lesions compared to the smallest tumor measurement obtained either at baseline (if no decrease) or best response, on stable or increasing doses of corticosteroids.*
 - 1. b) Significant increase in T2/FLAIR non-enhancing lesion on stable or increasing doses of corticosteroids compared to baseline scan or best response following initiation of therapy,* not due to co-morbid events (radiation therapy, demyelination, ischemic injury, infection, seizures, postoperative changes, or other treatment effects).
- c) Any new lesion.
- d) Clear clinical deterioration not attributable to other causes apart from the tumor (e.g., seizures, medication adverse effects, complications of therapy, cerebrovascular events, infection, etc.) or changes in corticosteroid dose. The definition of clinical deterioration is left to the discretion of the treating physician, but it is recommended that a decrease in 20% of KPS or from any baseline to 50% or less be considered, unless attributable to comorbid events.
- e) Failure to return for evaluation due to death or deteriorating condition.
- f) Clear progression of non-measurable disease.

* Stable doses of corticosteroids include patients not on corticosteroids.

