3.2 Safety population

All patients who received at least one full or partial dose of BAL101553 and had at least one post-baseline safety assessment must be included in the safety analysis populations. The safety analysis population will be used for all safety related analyses (AEs, vital signs, laboratory data, etc.).

Patients will be primarily analyzed according to their originally-assigned dose level.

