5.2 Efficacy analysis

5.2.1 Overall survival

OS is defined as the time from Day 1 dosing to the date of death. Patients who have not died at study closure will be censored at the time of last known alive.

OS will be summarized for the safety population overall. The median time to death, as well as 25th and 75th percentiles, will be determined by Kaplan-Meier method. Its 95% CI will be performed using the Brookmeyer-Crowley method. The associated survival curve will be displayed.

OS will be listed by dose level and patient.

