5.2.2 Progression-free survival

PFS is the interval between Day 1 dosing and the earliest date of progression or death due to any cause in the absence of progression. Patients who have not progressed or died at study closure will be censored at the time of their last assessment without progression.

If a patient has no post-baseline progression assessment, the PFS will be censored to 0 days.

PFS will be summarized for the safety population overall. Same statistics and curves than for OS will be displayed.

PFS will be listed by dose level and patient.

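### The 0-day censoring sentence in SAP 5.2.2 has no vital-status condition, so read literally it removes a known death from PFS that still counts for OS

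*SAP*

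**What the plan says.** SAP 5.2.2 contains three rules that bear on a patient with no post-baseline progression assessment.

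1. PFS runs from Day 1 dosing to "the earliest date of progression or death due to any cause in the absence of progression". Death without progression is therefore an event.
2. The general censoring rule is limited to event-free patients: "Patients who have not progressed or died at study closure will be censored at the time of their last assessment without progression".
3. A further sentence, set as its own paragraph, reads: "If a patient has no post-baseline progression assessment, the PFS will be censored to 0 days". It states no condition on vital status.

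For survival, SAP 5.2.1 states: "OS is defined as the time from Day 1 dosing to the date of death". No progression assessment is needed for a death to count there. PFS and OS are both summarised for the safety population, all dose levels pooled.

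**The concern.** Rules 1 and 3 give opposite answers for one kind of patient: treated, in the safety population, dead, with no post-baseline progression assessment and no progression entered in the CRF. Rule 1 makes this an event on the date of death. Rule 3, taken as written, makes it a censored observation at time zero.

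A patient censored at time zero is in no Kaplan-Meier risk set at any event time, so the literal rule deletes a known event and its patient from the estimate. If the death falls before the median, the reported median is too long. The same death remains in OS, so the two endpoints would disagree about one patient. PFS is a stated secondary objective, and with 26 patients one reclassified event visibly moves the curve.

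**Working it through.** **Does any other text settle precedence?**

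- Protocol 11.3 names progression alone as the PFS endpoint. It cannot confirm that death overrides the 0-day rule.
- SAP section 6 lists changes to the time origin and to which estimates are shown. It does not mention this rule.
- Protocol Appendix III lists under progressive disease: "Failure to return for evaluation due to death or deteriorating condition". That would turn such a death into a progression. However, SAP 4.1 takes progression status as reported in the CRF, so this helps only if the site enters it.

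None of them does.

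**Can such a patient exist?** The safety population takes in patients who were dosed and "had at least one post-baseline safety assessment must be included in the safety analysis populations". That is a safety assessment, not a progression assessment, so a patient seen at a weekly visit who then dies stays in the PFS set. A patient without even that visit is outside PFS on either reading. MRI is scheduled at baseline and 10 weeks (Protocol 4.2.2), and the only scheduled on-treatment neurological examination is Day 22 (Protocol 9.1). Protocol 10.2 allows survival status to come from a phone call or records, so a death can be known without an assessment. The case is possible but narrow.

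**One patient under both readings.** Suppose death on day 45 with no progression assessment. OS: event at 45 days (46 if a day is added). PFS by rule 1: event at the same time. PFS by rule 3: censored at 0.

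**Size: illustration only.** The plan gives no PFS figure to reproduce.

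- From the documents: n = 26 (SAP 2.4.2).
- Assumed: k = 1, 2 or 3 such deaths, all before the median; exponential PFS with hazard λ in the other 26 − k patients; no other censoring.

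Literal rule: only the 26 − k patients contribute, so the median is ln 2/λ.

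Deaths counted: the curve after the k deaths is [(26 − k)/26]·exp(−λt). Setting this to 0.5 gives a median of [ln 2 + ln((26 − k)/26)]/λ.

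| k | ln((26 − k)/26) | Counted ÷ literal | Literal above counted |
|---|---|---|---|
| 1 | −0.0392 | (0.6931 − 0.0392)/0.6931 = 0.943 | 6.0% |
| 2 | −0.0800 | (0.6931 − 0.0800)/0.6931 = 0.885 | 13.1% |
| 3 | −0.1226 | (0.6931 − 0.1226)/0.6931 = 0.823 | 21.5% |

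If one such death falls after the median, the counted median solves (25·exp(−λt) + 1)/26 = 0.5, so λt = −ln(12/25) = 0.734. The literal median is then 0.6931/0.734 = 0.944 of it, about 6% too short.

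**Simulation** (40,000 runs per setting; deaths uniform on 0.3 to 2.2 months; assumed median of 7 months in the other 26 − k patients):

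| k | Literal, months | Counted, months | Mean difference | SD of literal median | Difference/SD |
|---|---|---|---|---|---|
| 1 | 7.19 | 6.80 | 0.39 | 2.03 | 0.19 |
| 2 | 7.24 | 6.43 | 0.81 | 2.04 | 0.40 |
| 3 | 7.20 | 5.98 | 1.22 | 2.12 | 0.58 |

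Across assumed medians of 6 to 9 months the ratio of the two medians was 1.057–1.058, 1.126–1.127 and 1.204–1.207 for k = 1, 2, 3, close to the closed form.

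**A fixed data set.** Take deaths at day 30, then 45, then 60, with the other patients at exponential quantiles with median 180 days. PFS at day 70, counted versus literal, is 73.1% vs 76.0% (k = 1), 69.2% vs 75.0% (k = 2) and 69.2% vs 78.3% (k = 3). For k = 1, taking the median as the first time the curve reaches 0.5 gives 160 vs 180 days, a 12.5% gap. The curve sits exactly at 0.5 between days 160 and 180, however; averaging those gives (160 + 180)/2 = 170, and 180/170 = 1.059, which matches the closed form.

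**The case against.** The strongest reply is that the paragraph is coherent when read in order. Rule 2 dates censoring at the last assessment for patients without an event, which leaves one gap: an event-free patient with no assessment. Rule 3 comes next and fills that gap. This is probably what was meant, and the paragraph break is weak evidence against it, since line breaks in text extracted from a PDF are unreliable. Even so, rule 2 carries its condition explicitly and rule 3 does not, and a program should not depend on inferred intent.

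The second reply is that the group is very small. Progression can be clinical as well as radiological, so the Day 22 neurological examination (±3 days) may count as a progression assessment and close the window by Day 25. On stopping treatment, "Evaluations are to be performed within the 7 days following the off-treatment date, unless indicated", and at withdrawal "a final evaluation of the subject should be performed". Two-monthly follow-up comes after that. This stands as a limit on size. It does not remove the case: the SAP does not define a progression assessment, and a patient who dies on treatment cannot attend these later visits. If only MRI counts, the window runs to about week 10.

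The third reply concerns the illustration, and it is fair. Nothing in the documents supports k = 2 or 3. About 73% of the simulated death times fall after Day 25, (2.2 − 0.82)/1.9, when the patient would normally have been examined. That does not alter the ratios, but it makes more than one such death less plausible. The 7-month median also belongs to the other patients; with the deaths included, the closed form gives 6.6, 6.2 and 5.8 months. The percentages are not an expected bias.

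**Conclusion.** The concern holds as a minor defect. As written, the 0-day sentence contradicts the event definition in the same section for a patient known to have died without a progression assessment, and nothing else in the documents resolves it.

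The effect is nil if there is no such patient. With one death before the median, the literal rule overstates median PFS by about 6%. That is well inside the sampling variation: the simulated 95% range of the literal median is about 3.8 to 11.7 months. The size rests on an assumed number of deaths and exponential PFS; the contradiction rests on neither. The PFS listing by patient would show a 0-day censored time for a patient with a recorded death, so the error could be noticed.

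**What to change.** Reword the sentence in SAP 5.2.2 along these lines: a patient without any progression assessment after baseline, and not known to have died, is censored at 0 days; a death without documented progression is a PFS event on the date of death, whether or not progression was ever assessed.

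Report how many patients fall into each of two groups: those censored at 0 days, and those whose PFS event is a death with no prior progression assessment.

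The cost is one clause and one condition in the derivation program. Dates of death are already needed for OS, and results do not change if no such patient exists.

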5.3 Pharmacokinetic analysis

Individual subject plasma concentration-time curves will be analyzed by noncompartmental methods. PK parameters will be presented as listings and descriptive summary statistics by dose groups and PK days. Individual and mean cohort plots of

concentration versus time will be constructed. Dose proportionality will be evaluated using the power model.

Pharmacokinetic parameters and variables will be calculated for BAL101553 (if applicable) and BAL27862 according to standard equations using actual sampling times if available.

Following administration, C_{max} and T_{max} will be obtained directly from the experimental observations. If multiple maxima occur at equal concentrations, the first temporal value will be taken.

AUC will be calculated using the linear up/log down trapezoidal rule, using actual elapsed time since the start of oral administration.

The number of data points included in the regression for determination of λz and $t^{1/2}$ after single-dose will be determined by visual inspection, but a minimum of 3 data points in the terminal phase, excluding C_{max} , will be required to estimate λz . The λz values (and consequently $t^{1/2}$, CL/F , Vd/F and AUC_{inf}) will be considered unreliable estimates if the time period over which an individual λz was estimated is less than twice the resultant $t^{1/2}$ or if the adjusted coefficient of determination 'Rsq' is less than or equal to 0.75.

The proportion of AUC_{inf} due to extrapolation (AUC_{extrap}) will also be calculated and expressed as a percentage. The value of AUC_{extrap} should be less than or equal to 20% for AUC_{inf} to be considered to be well estimated. If AUC_{extrap} is higher than 20%, then the values of AUC_{inf} , CL/F , and Vd/F will be considered unreliable and therefore excluded from the summaries.

5.4 Safety analysis

Safety assessments will be conducted throughout the entire study period. Analyses will be performed using safety population, unless otherwise specified.

The safety evaluations will include analyses of adverse events, laboratory assessments (hematology, biochemistry, cardiac troponin, and coagulation), ECG, magnetic resonance imaging (MRI) scan, and vital signs.

5.4.1 Dose-limiting toxicity

The DLTs will be listed by dose level and patient.

5.4.2 Treatment exposure and radiation therapy

The duration (in days) of BAL101553 exposure, the actual dose received, and treatment compliance (as collected in the CRF), will be listed by patient and summarized using descriptive statistics by dose level.

Any other treatment exposure information will also be included in the listing.

Study drug dose interruptions and reductions will be listed by patient.

The duration (in days) of radiation therapy, the actual dose, and percentage (as collected in the CRF) received will be listed by patient and summarized using descriptive statistics by dose level.

Any other radiation therapy information will also be included in the listing.

5.4.3 Adverse events

Treatment-emergent events are defined as all events occurring after BAL101553 treatment begins. Any adverse event starting prior to the first study drug administration will be reported as medical history. The relationship of an AE to study drug and RT is recorded as unrelated, unlikely, possible, probable, or definite.

For analysis purposes, ‘related to BAL101553’ AEs will be those reported as possible, probable, definite, or those for which the relationship is unknown.

Adverse events will be presented in data listings including dose level, patient, dates/times, study day of event, MedDRA SOC, PT, duration of the event, seriousness, CTCAE grade, intensity, drug adjustment, treatment taken, relationship to study drug, relationship to RT, and outcome.

An overview table (including only treatment-emergent AEs) will also be presented with the number (and percentage) of patients and number of events with:

- Any AE
- Related to BAL101553 AEs
- CTCAE grade 3/4 AEs
- CTCAE grade 3/4 related AEs
- SAEs
- Related SAEs
- AEs leading to dose modifications (i.e., dose reduced or dose interrupted)
- Related AEs leading to dose modifications (i.e., dose reduced or dose interrupted)
- AEs leading to study drug discontinuation
- Related AEs leading to study drug discontinuation
- AEs leading to death
- Related AEs leading to death.

This table will be displayed by dose level.

All treatment-emergent AEs and treatment-emergent AEs related to treatment will be summarized by incidence rate tables broken down by:

- SOC and PT.
- SOC, PT, and worst CTCAE grade.
- SOC, PT, and drug relationship.

Serious treatment-emergent AEs, treatment-emergent AEs leading to dose modifications, leading to study drug discontinuation, or leading to death will be also summarized by SOC and PT. The same analyses will be repeated for related AEs.

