4.1 Study Design

Figure 5 Schema

This study will define the MTD of daily oral BAL101553 when given in combination with standard RT (60 Gy in 30 daily fractions, M-F) in patients with newly diagnosed *MGMT* promoter unmethylated GBM.

Following tumor resection, patients will begin an assigned BAL101553 dose in combination with the standard 6 weeks of radiation. The starting dose of BAL101553 will be 4 mg per day, i.e. approximately 25% of the MTD of oral BAL101553 in the solid tumor arm of Phase I clinical study CDI-CS-002 in patients with solid (non-brain) cancers, which is ongoing in Europe. 8 mg/day was the starting dose in the ongoing GBM arm of study CDI-CS-002.

Oral BAL101553 will be given once daily (7 days per week) for 6 weeks, concurrent with standard RT. This will be followed by a 4-week no-treatment period. The duration of study treatment will be defined as these 6 weeks of treatment plus the 4 weeks of rest. The safety evaluation period is the 10 weeks from start of treatment.

[figure not shown]
There is approximately a 20% progression rate during the first 10 weeks from initial diagnosis among patients with newly diagnosed GBM (Hegi 2005²⁰, and unpublished data). Patients or treating physicians may request early withdrawal from the trial prior to the patient completing the 10 weeks of treatment or the evaluation period, due to disease progression or reasons other than toxicity. Therefore, to prevent unreasonable delay in completing each cohort, five patients will be enrolled onto a dose cohort to ensure 3 evaluable patients at the end of the 10-week treatment period. The standard 3+3 design will be used for dose-finding. Dose escalation will be done in a stepwise fashion. As a precautionary measure, subsequent patients at each new dose level may only be dosed after

confirmation of safety in the first patient over the first 3 weeks of treatment. The target DLT rate is 33%.

After the 4-week rest period following the 6 weeks of treatment, patients will be off study treatment and should continue standard-of-care treatment with adjuvant TMZ and appropriate follow-up.

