9.2 Adverse Events

Patients will be evaluated for safety if they have received at least one dose of BAL101553.

The timely reporting of AEs (including deaths) is required by the U.S. Food and Drug Administration. The reporting of toxicities is part of the data reporting for this study. Adverse events will be collected for at least 30 days following the last dose of study drug. Beyond this time point only newly occurring adverse events that are serious and drug-related will be recorded.

Adverse events must be reported to the ABTC Central Office and the NCI by the investigative site in the manner described and per the requirements of the clinical site's IRB.

Adverse events will be entered into CTEP's iMedidata Rave database by the investigative site in a timely manner. See Section [12.4 – Data Collection/Reporting](#).

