9.3.2 Expedited Adverse Event Reporting

➤ **Use CTEP-AERS Web Application and Document on ABTC AE Form**

- All SAEs that occur from the time of the first administration of study drug until 30 days after the last study treatment must be documented on both the ABTC AE form and using the CTEP-AERS Web Application within 24 hours of learning of the event. SAEs beyond 30 days after last study treatment must be documented on both the ABTC AE form and using the CTEP-AERS Web Application within 24 hours of learning of the event if these events are considered to be causally related to study treatment.
- Expedited AE reporting for this study will use CTEP-AERS (CTEP AE Reporting System), accessed via the CTEP web site (<https://eapps-ctep.nci.nih.gov/ctepaers>). In the rare occurrence when Internet connectivity is lost, a 24-hour notification is to be made to the ABTC Central Office by telephone at [REDACTED] Once Internet connectivity is restored, the 24-hour notification must be entered electronically into CTEP-AERS by the original submitter at the site.
- All SAEs reported through the Web Application are automatically sent to the ABTC Central Office. The pharmaceutical Sponsor, Basilea, will be notified by ABTC Central Office when an SAE is reported through CTEP-AERS (within 24 hours). All SAEs will be documented and tracked by Basilea as well as through the ABTC Central Office. Queries and follow up required for completing all SAEs will be conducted through Basilea and the ABTC Central Office in a timely fashion. When an expedited report is required (7/15 days), a speedy resolution of queries will be expected in order to allow for on-time reporting to the FDA. Basilea is responsible for reporting all applicable SAEs to the FDA.

ABTC # 1601

NCI # ABTC-1601

PI: [name]

- All SAEs (related or unknown relationship to study drug) will be followed until satisfactory resolution or until the Investigator deems the event to be chronic or the subject to be stable. Withdrawal from the study and all therapeutic measures will be at the discretion of the Investigator.

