9.3.3 SAE Reporting

Any SAE, as described in Section [9.3.1](#), including death due to any cause, which occurs during this study must be **reported immediately (within 24 hours)** to the ABTC Central Office.

A phone call must be made to:

ABTC Manager: [REDACTED]

Basilea will be responsible for reporting of any SAE to the FDA as required by legislation. Basilea will notify the FDA of any unexpected, fatal or life-threatening experience (expedited report) associated with the use of study drug as soon as possible but no later than 7 calendar days after the initial receipt of the information. Initial notification will be followed by a written report within 15 calendar days. For other unexpected serious events (i.e. that are not fatal or life-threatening) associated with the use of study drug, Basilea will notify the FDA as soon as possible, but no later than 15 days, of the initial receipt of information.

These events also must be reported by the Investigator to the appropriate IRB.

Patients who are removed from study due to AEs should be followed until the AE has resolved or stabilized. Copies of relevant documentation, such as laboratory reports, should be kept with the patient's study records.

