10.2 Off-Study Criteria

Patients will only be off study at the time of death. Patients will be followed every two months for progression, for up to one year from the off-treatment date. All patients will be followed for survival every 2 months for the first 2 years from the off-treatment date; after 2 years, patients will be followed every 6 months until death. Survival status may be obtained by phone call, clinic visit, or medical records (e.g. physician notes/laboratory results of clinic or hospital visit).

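### The SAP's treatment-emergent definition has no end date and the protocol has two rules for late SAEs and deaths, so all-cause safety rows can collect post-treatment events unevenly

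*SAP*

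**What the plan says.** **SAP 5.4.3.** "Treatment-emergent events are defined as all events occurring after BAL101553 treatment begins". No closing date follows. The definition feeds the overview table by dose level (any AE, grade 3/4 AEs, SAEs, AEs leading to death, each with a related counterpart where one applies) and the tables by SOC and PT.

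**Protocol 9.2.** "Adverse events will be collected for at least 30 days following the last dose of study drug". Then: "Beyond this time point only newly occurring adverse events that are serious and drug-related will be recorded".

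**Protocol 9.3.2.** SAEs more than 30 days after the last treatment go on the AE form and into CTEP-AERS only "if these events are considered to be causally related to study treatment".

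**Protocol 9.3.3.** Any SAE, "including death due to any cause, which occurs during this study must be" reported to the Central Office within 24 hours. No time or causality limit is given.

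**Protocol 10.2** (repeated in SAP 2.4.1). "Patients will only be off study at the time of death".

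**Protocol 4.1.** After the 4-week rest, "patients will be off study treatment and should continue standard-of-care treatment with adjuvant TMZ and appropriate follow-up".

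**The concern.** A treatment-emergent rule needs two ends. With only a start, the analysis takes whatever is in the AE dataset, and the protocol gives sites two different rules for what goes in late. A site working from 9.2 and 9.3.2 leaves out a hospitalisation for progression at month six. A site working from 9.3.3 reports it, and if it is entered as an AE the SAP tabulates it as treatment-emergent to BAL101553.

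The by-dose safety tables are the main output for the safety secondary endpoint. If their all-cause rows depend on which section a site followed, on how long a cohort has been followed, and on what was given after week 10, then a difference between dose levels need not reflect the drug.

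**Working it through.** The plan states no figure to reproduce. The check sets the texts side by side and then applies calendar arithmetic to the plan's own schedule.

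**1. Does the SAP supply an end elsewhere?** SAP 2.3 describes the 6 + 4 weeks and says safety data are collected over that period. SAP 5.4 refers to the entire study period. SAP 2.4.1 keeps patients on study until death. None of these is written as a limit on the 5.4.3 definition, and they do not point to one date.

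**2. What can reach the AE dataset late?**

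| Protocol section | Events more than 30 days after last dose |
|---|---|
| 9.2 | New, serious and drug-related only |
| 9.3.2 | SAEs only if causally related |
| 9.3.3 with 10.2 | Any SAE and any death, until death |
| 9.4 | All AEs go into routine data, with no time limit stated; CTEP-AERS reports are named explicitly |

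Under the first two rows, late unrelated events stay out. Under 9.3.3 read literally, they have a route in through 9.4.

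**3. Overlap with temozolomide when 9.2 is followed.** Inputs: 42 days of dosing and 28 days of rest (Protocol 4.1), a 49-day limit if RT runs long (4.4.1), 30 days of AE collection (9.2), and a +14-day allowance on the 30-day visit (9.1, note 12). Temozolomide is taken to start as soon as the rest ends.

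- Last dose Day 42: rest ends 42 + 28 = 70; 30-day point 42 + 30 = 72; latest visit 72 + 14 = 86. Overlap: 72 − 70 = **2 days**, up to 86 − 70 = **16 days**.
- Last dose Day 49: rest ends 77; 30-day point 79; latest visit 93. Overlap: 79 − 77 = 2 days, up to 93 − 77 = 16 days.
- In general, if new therapy starts *k* days after the last dose, the overlap is 30 − *k* days, or up to 44 − *k* with the visit window. For a patient who stops early and starts other therapy at an assumed *k* = 14, that is 16 days, or up to 30.

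The upper figures assume that a late visit records all events up to its own date. The words at least in 9.2 permit this but do not require it.

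**4. Scale if 9.3.3 were followed literally.** The documents give no survival figure, so this is an illustration on assumed inputs: exponential survival from Day 1, median *m* = 8 to 16 months, 26 patients (SAP 2.4.2), last dose Day 42. Expected deaths by day *d* = 26 × [1 − 2^(−*d*/(30.4375 *m*))].

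| Assumed median | By Day 72 | By Day 365 | Difference |
|---|---|---|---|
| 8 months | 4.8 | 16.8 | 12.0 |
| 16 months | 2.5 | 10.5 | 8.0 |

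So within one year the two rules could differ by about 8 to 12 deaths out of 26 if every site entered every death as an AE, and by none if no site did. The real difference depends on site practice.

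**5. Unequal follow-up by dose.** SAP 2.4 puts at least 10 weeks between the last accrual at one level and the first at the next. If all five levels opened (the documents do not say), level 5 started at least 4 × 10 = 40 weeks after level 1 finished accruing. With an open window and a common data cut-off, the lower doses have longer to accumulate late events.

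**6. Which rows move?** Late unrelated deaths add to SAEs and AEs leading to death. Late unrelated hospitalisations add to SAEs and, if so graded, to grade 3/4 AEs. Rows for related events change only if the event is judged possible, probable or definite, or if its relationship is unknown, which SAP 5.4.3 counts as related.

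**The case against.** The strongest reply is that a table can hold only what is recorded. Protocol 9.2 and 9.3.2 both close unrestricted recording at 30 days, the schedule in Protocol 9.1 ends AE evaluation at the 30-day visit, and later follow-up is for progression and survival. This stands: if sites follow those sections, most late unrelated events never reach the dataset.

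Section 9.3.3 can also be read more narrowly. Protocol 4.2.2 uses study period for the 10 weeks, 9.3.3 describes a telephone report, and the AE definition in 9.2.1 requires a temporal association with treatment. These are fair readings, but the text does not choose among them, and 10.2 supports the wide one.

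The consequences are limited too. The tables are descriptive, related rows sit beside all-cause rows, and the listings give study day and attribution. That also stands. Post-baseline therapies are listed under SAP 5.4.8, but the Protocol 9.1 schedule shows medication recording only up to the off-treatment visit, so temozolomide start dates may be incomplete.

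Three stronger readings are tempting, and the documents do not support them:

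- *AEs leading to death will approach all 26 patients.* That needs the literal 9.3.3 at every site, entry of each report as an AE against 9.2, and follow-up of everyone to death. It is a ceiling, not a forecast.
- *The overlap reaches 23 days after a Day 49 last dose.* 93 − 70 = 23 counts from Day 70, but the 4-week rest then ends on Day 77, so the figure is 16.
- *The MTD is at risk.* DLTs are assessed over the 10-week period in their own population (Protocol 4.2.2, SAP 3.4), so this definition does not enter.

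**Conclusion.** The point holds as a definitional gap of moderate weight that should be closed before database lock. The SAP rule is open-ended, and Protocol 9.3.3 conflicts with 9.2 and 9.3.2 on late unrelated SAEs and deaths. Together they let all-cause rows for SAEs, grade 3/4 AEs and AEs leading to death vary with site practice and length of follow-up.

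The part that does not depend on 9.3.3 is small: about 2 days of temozolomide overlap at the 30-day point, up to 16 with the full visit window, and more after early stopping. This assumes temozolomide starts directly after the rest. The part that depends on 9.3.3 ranges from nothing to a substantial share of deaths, and the documents do not show where in that range the trial lies.

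**What to change.** **SAP 5.4.3.**

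- Define treatment-emergent as onset from the first dose of BAL101553 through 30 days after the last dose, matching Protocol 9.2.
- Do not add a Day 70 minimum. For a patient whose last dose is Day 20, full recording is guaranteed only to Day 50, so a Day 70 floor would mix two recording rules.
- Flag events that start on or after the first dose of temozolomide or other new anticancer therapy.
- Put all later events, including late related SAEs, in a separate table or listing.

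**Protocol 9.3.3.** Reconcile it with 9.2 and 9.3.2 so that one rule decides which late SAEs and deaths enter the AE dataset. Deaths remain captured in overall survival either way. The SAP cut-off works on its own even if this text is left unchanged.

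**Cost.** One definition, one date comparison, one flag and one extra output. The flag needs the start date of new therapy, so check that the CRF holds it after the off-treatment visit. The SAP was written while the study was ongoing (SAP 1), so the rule could be fixed before lock. Changing 9.3.3 costs more, because it alters a reporting requirement with all 26 patients already included. The one analytic downside is small: a late drug effect would appear in the post-treatment output and not in the main table. No data are lost.
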